injection of Exparel can provide adequate pain relief over 3 days it can make obsolete the need to place a continuous nerve block catheter. There are significant benefits to this. It requires more skill and time to place a catheter versus a single injection of a local anesthetic for a TAP block. Other benefits are related to the avoidance of catheter maintenance including dressings, leakage at catheter insertion site, and the need for additional infusion pumps. Furthermore, any catheter has the possibility of infection or bleeding.

It is the purpose of this study to evaluate the efficacy of methods that allow for continuous release of local anesthetic in the TAP space, either via catheter or via injecting Exparel® a slow release liposomal space versus the standard single injection Bupivacaine in the TAP space. The study shall consist of three (3) arms of which patients will be randomly assigned: Continuous TAP block (CTAP) via Catheter, Single Injection TAP block with the slow release liposomal Exparel, and Single Injection TAP block with Bupivacaine. Several parameters will be measured with the primary goal being to determine the effectiveness and duration of post-operative pain relief.^{8,9}

Primary Hypothesis

Methods that allow for continuous release of local anesthetic in the TAP space will decrease total narcotic requirements vs. the standard single shot Bupivacaine control. A continuous release of local anesthetic in the TAP space via catheters over 2 days will result in lower total narcotic requirements when compared to the single shot Bupivacaine injection technique when measured over 48 hrs. The Liposomal agent Exparel® which releases the Bupivacaine local anesthetic over three days should also allow for a single injection technique that can provide similar post-operative pain response to that of the catheter method without the need to place a catheter in the TAP space. Post-operative narcotic requirements are inversely related to post-operative pain control and patient satisfaction and total narcotic requirements will be significantly higher in the single shot group vs. the continuous release groups over 48 hrs.

Purpose of the Study Protocol

The purpose of this study protocol is to ensure consistent implementation of this study across all study sites.

B Background

Prior Literature and Studies

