Although, there is a fair amount of literature and case reports for TAP block for post-op pain; there is very little data that goes out as far as 72 hrs. Furthermore, those studies (albeit limited) demonstrate a difference that is not considered statistically significant between single shot TAP block and controls that did not receive TAP block at 72 hrs. Studies do however show a statistically significant difference in narcotic requirements and pain scores at 24 hrs (post-operative day [POD] #1), and at 48hrs (POD #2) between single shot TAP and placebo^{4,12} and also between continuous TAP techniques and placebo¹³. However, no direct comparison study exists between continuous TAP Block techniques and standard single shot Bupivacaine technique. Using prior studies as a reference and making the appropriate equianalgesic conversions to account for the difference in narcotic potencies used in the various studies we can come to the expectation that total hydromorphone (Dilaudid) requirements would be roughly 50% lower in the continuous catheter TAP technique vs. the standard single shot Bupivacaine TAP technique at 48hrs. We estimate total Hydromorphone requirements over 48 hrs. in the control (single shot TAP) to be equal to 4.1mg versus the continuous catheter TAP group equaling 2.4 mg. We would also assume Exparel TAP to be equal to catheter TAP at 2.4 mg. Furthermore, Visual Analog Scales as expected follow a similar trend, with the most significant difference seen at 48 hrs.^{4,11-13}

Rationale for this Study

The rationale for this study is to examine the post-operative pain benefits of continuous release TAP techniques (Catheter technique and liposomal slow release Exparel® technique) versus the

standard single shot Bupivacaine injection for TAP block. Therefore, in this study the standard single shot Bupivacaine technique acts as the control.

Although both modalities of continuous release TAP block have been proven versus placebo to provide post-operative pain relief over an extended time period; there is no such study that directly compares the standard single shot Bupivacaine technique to the continuous release TAP techniques in terms of quality or ability to control post-operative pain. Given the significant increased cost along with in the case of the catheter group skill, procedural time, and maintenance management there should be a significant improvement in post-operative pain duration versus the single shot Bupivacaine TAP block technique.

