
Furthermore, our expectation is that this difference will be most apparent at 48 hrs. as discussed above with a reduction in narcotic requirements greater than 40% in the continuous catheter TAP group vs. standard single shot Bupivacaine TAP (4.1 mg +/- 3 mg vs. 2.4 mg +/- 1.3 mg Dilaudid). This is based on the assumption that the effects of the local anesthetic control TAP (single shot Bupivacaine) may last up to 24 hrs. At 72 hrs, prior studies, although limited, have not shown a significant difference between TAP block and placebo groups.

c Study Objectives

Primary Aim

The primary aim is to evaluate for any significant difference total post-operative narcotic requirements (Dilaudid) required over 48 hrs. in the continuous catheter TAP block arm vs. the single shot Bupivacaine TAP arm and again the slow release Liposomal Exparel® TAP arm vs. the single shot Bupivacaine TAP arm.

Secondary Aim

The secondary aim will be to evaluate for any significant difference in narcotic requirements at other endpoints such as 24 hrs and at 72 hrs. As discussed before, current studies do not show a significant difference when extrapolated out at those end points, albeit there is very little data at 72 hrs. Other quality indicators of recovery in the three arms such as Visual Analog Scores (VAS) are expected again to be most significantly different at 48 hrs. Other quality measures that will be recorded include incidence and severity of post-operative nausea and vomiting (PONV), time to ambulation, and patient satisfaction with post-operative pain control.

Rationale for the Selection of Outcome Measures

Outcome measurements are based on the assumption that narcotic requirements (i.e. intravenous Dilaudid Patient-Controlled Analgesia [PCA] use) are inversely related to patient satisfaction in regards to their post-operative pain. Additional factors such as VAS, ambulation, performance of daily activities, and anti-emetic pharmaceutical requirements have been chosen as quality indicators in regards to post-operative pain control and dependence on narcotics.

D Investigational Agent

This investigation will use three FDA-approved techniques:

- Bilateral Continuous TAP block via Catheter (One-time bolus of Bupivacaine 0.25% x 20ml per side followed by continuous infusion of Ropivacaine 0.2% 7 ml/hr. per side x 48 hrs.);
- Single Injection TAP block with Exparel® (One-time bolus of Bupivacaine 0.25% x 20 ml followed by Exparel 133 mg per side); and

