F3.d Data Collection Procedures for Adverse Events

Please see Attachment L2 for data collection form. All adverse event data will be entered into Oncore ERM.

F3.e Reporting Procedures

Serious Adverse Events and adverse events that meet "severe" criteria must be directly reported within 24 hours to the Principal Investigator, and the IRB.

[name] M.D.
[contact]
[contact]
Department of Anesthesiology
Midwestern Regional Medical Center
Zion, IL

Other adverse events must be entered within 7 days of collection into the Oncore ERM.

F3.f Post-study Adverse Event

Serious Adverse Events and adverse events that meet "severe" criteria must be directly reported within 24 hours to, the Principal Investigator and the IRB.

[name] M.D.
[contact]

[contact]
Department of Anesthesiology
Midwestern Regional Medical Center
Zion, IL

Other adverse events must be entered within 7 days of collection into the Oncore ERM.

F3 Study Outcome Measurements and Ascertainment

G Statistical Plan

Interim Monitoring and Early Stopping

The Principal Investigator will utilize the Oncore ERM study management system to monitor the study.

The study may be stopped early for the following reasons:

- withdrawal of funding
- safety issues
- drug has been proven effective and no further testing is needed

Analysis Plan

The study is a prospective, randomized, open, active controlled clinical trial. Effectiveness of the Continuous TAP (CTAP) via the ON-Q[®] Pain Management System will be evaluated and compared to single shot techniques with respect to reductions in postoperative opioid consumption over the first 72 hours postoperatively. Secondary outcomes including hospital length of stay (LOS), time in PACU, pain at rest and with activity, return of bowel function, and incidence of opioid related side effects will also be evaluated.

The aims of this study are to compare the efficacy of continuous TAP block via ON-Q[®] system versus that of single injection techniques for TAP block regarding opioid reduction among patients undergoing major abdominal surgery. It is hypothesized that a continuous TAP block technique reduces pain, the need for opioids as well as the expected length of stay relative to those resulting from those subjects receiving a single TAP injection of Exparel (liposomal Bupivacaine) or single TAP injection of Ropivacaine to treat postoperative pain.

Study success criteria:

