Based on the above hypothesis this study will be considered successful in demonstrating superior efficacy relative to control if consumption of opioids postoperative is significantly less among patients randomized to receive a

continuous TAP block via the ON-Q[®] system compared to the patients randomized to receive a single TAP injection of Exparel (liposomal bupivacaine) or single TAP injection of Ropivacaine to treat postoperative pain. However, a finding of no difference between the continuous catheter technique and the Exparel arm would also be considered beneficial to the advancement of post-operative pain control techniques because it would demonstrate similar post-operative pain control can be achieved without the extra time and skill required to place a catheter.

Statistical Methods

Sample Size

The main objective of study is to compare total opioid consumption between the single shot TAP group and the Exparel TAP group with a parallel design. Based on previous studies and internal pilots, the mean total opioid consumption (standard deviation) was 4.1 mg (SD 3 mg) in single shot group and 2.4 mg (SD 1.3 mg) in Exparel TAP group. For the sample size calculation, a standard deviation of 3 is used as a conservative estimate. To detect a difference in mean opioid consumption between treatment groups, 4.1 mg vs. 2.4 mg, a sample size of 49 patients per arm is required to achieve 80% power with a significance level of 0.05 using a two-sided t-test or Wilcoxon rank-sum test depending on normality test. A secondary aim is to examine a difference in mean opioid consumption between the single shot TAP group and continuous TAP group. Allowing for a 10% dropout rate, a total of 159 participants with 53 participants in each arm will therefore need to be recruited into the study. It anticipated that approximately 8 participants per week will be enrolled into this study, thus the estimated accrual time is around 1 year.

Statistical Analysis Plan

All analyses will be conducted on patients following an intention-to-treat principle, including all randomized participants enrolled in three arms, in case of relevant non-compliance to the treatment and/or impossibility to evaluate the endpoints, a per-protocol analysis will also be performed, together with an analysis of non-compliance/non-evaluation.

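### The catheter success rule treats Exparel as a superiority comparator, leaves its 'or' undefined, and omits the comparison the trial is powered for

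*Combined protocol and SAP*

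**What the plan says.** Section G, Analysis Plan, sets the direction: "It is hypothesized that a continuous TAP block technique reduces pain, the need for opioids as well as the expected length of stay", relative to Exparel or the other single injection. Study success criteria then turns this into the only stated rule: "this study will be considered successful in demonstrating superior efficacy relative to control if consumption of opioids postoperative is significantly less among patients randomized" to the catheter, "compared to the patients randomized to receive a single TAP injection of Exparel (liposomal bupivacaine) or single TAP injection of Ropivacaine". The next sentence adds that finding no difference between catheter and Exparel would be a useful result too, because it would show that similar pain control is possible without a catheter.

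Other sections say something different:

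- The Primary Hypothesis expects that Exparel "can provide similar post-operative pain response to that of the catheter method".
- Section B, Prior Literature and Studies, plans on no difference between them: "We would also assume Exparel TAP to be equal to catheter TAP at 2.4 mg".
- Section B, Rationale for this Study, names the single shot bupivacaine technique as the control.
- Section G, Sample Size, makes Exparel versus single shot the main objective, with "4.1 mg (SD 3 mg) in single shot group and 2.4 mg (SD 1.3 mg) in Exparel TAP group". Catheter versus single shot is a secondary aim there.
- Section G, Statistical Analysis Plan, repeats that order and says only that catheter and Exparel will also be compared.

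**The concern.** The rule decides what the trial may claim, and it disagrees with the plan in three ways.

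1. It includes a superiority limb, catheter over Exparel, that the hypothesis and the planning value both treat as null.
2. It speaks of superiority over control, but one of its two comparators is not the control.
3. It leaves out the one contrast on which the sample size rests.

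In addition, the word 'or' can mean that the catheter must beat both arms, either arm, or the two injection arms taken together. The Analysis Plan's reference to single shot techniques as a group makes the pooled reading plausible. If the choice is left until the results are known, the same data could be called a success or a failure.

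**Working it through.** **Inputs.** Planned 48-hour means are single shot 4.1 mg, catheter 2.4 mg and Exparel 2.4 mg (section B, Prior Literature and Studies; section G, Sample Size). SDs are 3 mg for single shot and 1.3 mg for each continuous-release arm: "4.1 mg +/- 3 mg vs. 2.4 mg +/- 1.3 mg Dilaudid" for the catheter (section B, Rationale) and the same values for Exparel. For sizing, "a standard deviation of 3 is used as a conservative estimate". Alpha is 0.05 two-sided, allocation is equal, with 49 per arm needed and 53 recruited. After 10% dropout, 53 × 0.90 = 47.7, about 48, so n = 48 to 53 covers the plausible range.

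**The plan's own figure.** n per arm = 2 × [SD × (1.960 + 0.842) / difference]² = 2 × (3 × 2.802 / 1.7)² = 48.9, so 49. This reproduces. By the exact t-test, power at 49 is 79.3%.

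**Catheter versus single shot, n = 49.** SD 3: SE = 3 × √(2/49) = 0.606; 1.7 / 0.606 = 2.805; Φ(2.805 − 1.960) = 80% (79% by t-test). SDs 3 and 1.3: SE = √[(9 + 1.69)/49] = 0.467; 1.7 / 0.467 = 3.640; Φ(3.640 − 1.960) = 95%.

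**Catheter versus Exparel.** The planned difference is 2.4 − 2.4 = 0, so the chance that the catheter is significantly lower is 0.05 / 2 = 2.5% at any n or SD. For 80% power at n = 49 the true difference would have to be about 1.72 mg (SD 3) or 0.74 mg (SD 1.3 in both arms).

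**Pooled comparator.** The planned difference is (4.1 + 2.4)/2 − 2.4 = 0.85 mg, half of 1.7 mg.

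**The three readings.** Simulation of 400,000 three-arm trials per case, normal data, two-sided t-tests at 0.05, success only when the catheter is lower. Ranges run from n = 48 to n = 53.

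| Reading | SD 3 in all arms | SD 3 single shot, 1.3 others |
|---|---|---|
| Beat both arms | 2.5% | 2.5% |
| Beat the two arms pooled | 34–37% | 63–69% |
| Beat either arm | 78–82% | 95–96% |
| of which Exparel only | 0.02–0.03% | about 0.02% |

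The pooled row uses the equal-variance t-test. With an unequal-variance test its right-hand entry would be 78–82%.

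**All three arms truly equal (n = 49, SD 3).** P(either) = P(beat Exparel) + P(beat single shot) − P(both) = 2.5% + 2.5% − 0.45% ≈ 4.5%, against 2.5% for one contrast. About 2.0 points of the 4.5% come from beating Exparel only.

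**Assumed departure from plan.** Suppose the catheter equals single shot and Exparel is worse than both by 0, 0.5, 1.0 or 1.7 mg (n = 48, SD 3). The either-arm reading then declares success in 4.5%, 14%, 37% or 79% of trials. Nothing in the documents suggests Exparel would be worse; the range only shows what the wording permits.

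**The case against.** Three points can be made for the plan.

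First, the sentence after the rule foresees that the catheter and Exparel may not differ and does not count that as failure. This softens the conflict. It does not cure it, because no equivalence or non-inferiority margin is given and a non-significant difference does not show similarity. Nor does it say which comparison defines success.

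Second, the Statistical Analysis Plan tests each pair of arms separately, so a reader of the results would see which arm was beaten. That stands: the harm is a misleading success label, not an altered test. But nothing links those tests to the rule.

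Third, under the either-arm reading and the planned values, success comes almost wholly from beating single shot, which is the control. That also stands. A reader might infer that the rule gives a wrong conclusion however it is read, or that it would be met by beating the wrong arm. The documents do not support this: beating Exparel alone has a probability of about 0.03% under the planned means. A reader might likewise infer near-certain failure when both continuous-release methods work. That follows only if both arms must be beaten, and the 2.5% is then simply half of alpha at a true difference of zero.

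**Conclusion.** The point holds as a conflict within the plan. The success rule sets the catheter against an arm assumed equal to it, does not define 'or', and omits the powered primary comparison. Under the planning values the chance of success runs from about 2.5% to about 96%, depending on the reading and the SDs. Under the either-arm reading the usual conclusion would be right, but the wording still permits superiority over control without beating the control, and it raises false success in the catheter's favour from 2.5% to about 4.5% when all arms are equal.

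These figures rest on normal data and on the 48-hour planning means; the rule itself names no time window. Opioid totals are probably skewed, which would move the pooled and either-arm figures but not the roughly 2.5% or the conclusion.

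**What to change.** In section G, Analysis Plan and Study success criteria:

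- Remove Exparel as a superiority comparator for the catheter.
- Tie every superiority claim to the single shot control. Make Exparel versus single shot the primary success comparison, as powered, and catheter versus single shot the secondary one, each claimed only on its own contrast. Align section C, Primary Aim, which lists both contrasts as primary.
- Report catheter versus Exparel as a mean difference with 95% CI that plays no part in the superiority claim, and drop the statement that finding no difference would show similarity.
- Reconcile the name of the single injection comparator: section G says ropivacaine, sections D and E (Overview) say bupivacaine.

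The cost is a wording change, best made before any outcome data are analysed; it needs no new patients or data. The sponsor gives up two claims: the catheter cannot be called superior for beating Exparel, and a non-significant catheter–Exparel result cannot be presented as similarity.

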Patient characteristics and outcomes data will be summarized by cross-tabulation (categorical variables), quartiles (median, ordinal variables), and mean and standard deviation (continuous variables). Comparisons between groups will use Chi-square test or Fisher's exact test as appropriate for categorical variables and t-test or Wilcoxon rank-sum test as appropriate for continuous variables.

Analyses of primary outcome will examine differences in mean opioid consumption between the single shot TAP group and the Exparel TAP group. Analyses of secondary outcomes will examine differences in mean opioid consumption between the single shot TAP group and continuous TAP group. Treatment groups will be compared using a

student's t-test if data are normal distributed or Wilcoxon rank-sum test if not normal distributed.

The differences in mean opioid consumption across three groups (single shot TAP, continuous TAP, and Exparel TAP) will be examined with a test of means between groups using one-way analysis of variance (ANOVA). A comparison between continuous TAP and Exparel TAP will be performed. A t-test will be used if the observations in each trial arm are normally distributed; if non-normally distributed, then rank-based methods such as Wilcoxon rank-sum test will be employed.

All tests will be two-sided.

The overall incidence of serious adverse events and adverse events and number and proportion of patients reporting such events will be summarized by treatment group. Adverse events will be tabulated and summarized by the number and percentage of subjects who experienced the event.

Missing Outcome Data

Analysis will be conducted as described in prior section. Missing data will not be included in the analysis; however, may lead to an increase in patients recruited into one or more study arms.

Unblinding Procedures

This study is not blinded because it will be obvious to all care givers whether or not the patient received a continuous block with catheters or not.

H Data Handling and Record Keeping

Confidentiality and Security

Data will be collected on the data collection forms located in Attachment L9 and entered into the Oncore ERM study management system.

Data collection forms will be stored at each respective study site within a locked cabinet in a locked research office.

The Oncore ERM study management system is a secure web-based management system that is password-protected. Access to data is role-specific.

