All study sites will observe Health Insurance Portability and Accountability Act (HIPAA) Privacy and Security Rule standards.

Training

All research team members must complete approved Human Subjects and HIPAA training.

All research team members must complete Oncore ERM training.

Case Report Forms and Source Documents

Study sites will utilize the data collection forms in Attachment L9 to collect data and will enter data into the Oncore ERM study management system.

Records Retention

Paper study records will be maintained at the respective study sites for seven years from the end date of the study. At the end of this time period, study records will be shredded.

Data in the Oncore ERM study management system will be stored for seven years from the end date of the study. At the end of this time period, records will be deleted.

Performance Monitoring

The IRB and the Principal Investigator will monitor study performance using the Oncore ERM study management system.

I Study Monitoring, Auditing, and Inspecting

Study Monitoring Plan

The IRB and the Principal Investigator will monitor ongoing study performance using the Oncore ERM study management system.

Auditing and Inspecting

The IRB will audit and inspect study materials at the study sites as indicated.

J Study Administration

Organization and Participating Centers

The Principal Investigator at the lead institution will collaborate with study site Principal Investigators to oversee this study.

Funding Source and Conflicts of Interest

There are no conflicts of interest among any of the study investigators.

Study investigators must complete institution-specific conflict of interest forms as required.

Subject Stipends or Payments

Subjects will not be paid for their participation in the study.

Study Timetable

The study will last for approximately four months. This is the estimated time based on current operating room patient criteria to enroll ninety patients into the study.

κ Publication Plan

Upon completion of study and statistical methods, it would be expected to publish the study in an established and well-read peer journal of either Anesthesiology or Surgery. Given that an analysis demonstrating a statistically significant difference or no difference between any of the study arms would be useful to how anesthesiologist and/or the surgical team approach the TAP block, it is highly likely the study would be accepted for publication.

L Attachments – TAP Block Pain Management Data Form

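### The favourable reading of no difference between catheter and Exparel is not conditioned on either method beating single shot, so it cannot tell both working from neither working

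*Combined protocol and SAP*

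**What the plan says.** Study success criteria (section G) first ties success to significantly lower opioid consumption in the catheter arm than in the single-injection arms. It then adds that "a finding of no difference between the continuous catheter technique and the Exparel arm would also be considered beneficial", on the ground that "it would demonstrate similar post-operative pain control can be achieved without the extra time and skill required to place a catheter". That second statement names only the catheter and Exparel arms.

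The Statistical Analysis Plan makes Exparel versus single shot the primary analysis and catheter versus single shot a secondary one, and adds a three-group ANOVA. Separately, it says: "A comparison between continuous TAP and Exparel TAP will be performed". The method is an ordinary difference test: "A t-test will be used if the observations in each trial arm are normally distributed", with a rank-based test otherwise. It gives no margin, no definition of no difference, and no link from this comparison to the results against single shot.

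Two earlier sections treat single shot as the reference. The Primary Hypothesis pairs the expected Exparel-catheter similarity with lower narcotic use in both continuous-release groups than in the single shot group. The Rationale for this Study names single shot as the control and, citing added cost and (for the catheter) added skill, time and maintenance, says that "there should be a significant improvement in post-operative pain duration versus the single shot Bupivacaine TAP block technique".

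**The concern.** Two quite different outcomes produce the same catheter-versus-Exparel result. In one, both methods improve on single shot and Exparel can replace the catheter. In the other, neither improves on single shot. In the second case plain single shot is just as similar to the catheter as Exparel is, so the result gives no reason to choose Exparel over it. The stated interpretation drops the condition that the Primary Hypothesis attaches to the similarity, and so allows the same favourable reading in both cases.

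What is at stake is the conclusion about Exparel as a substitute for the catheter. As worded, a non-significant comparison of those two arms would be enough to support it.

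**Working it through.** **Inputs**
- Means of 4.1 mg (single shot) and 2.4 mg (Exparel), SDs of 3 and 1.3 mg, an SD of 3 used for planning, and 49 per arm: Sample Size.
- Catheter and Exparel assumed equal at 2.4 mg: Prior Literature and Studies. Catheter SD of 1.3 mg: Rationale for this Study.
- Significance level: Sample Size gives "80% power with a significance level of 0.05 using a two-sided t-test or Wilcoxon rank-sum test depending on normality test". It is stated only there; I assume that it also applies to catheter versus Exparel.
- Sidedness: "All tests will be two-sided".
- Assumption: no difference means a non-significant test.

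**The plan's own figure**

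n per arm = 2 × SD² × (1.960 + 0.842)² / difference² = 2 × 9 × 7.849 / 1.7² = 141.28 / 2.89 = 48.9, so 49. The plan's figure is reproduced. With the exact t-test, power at 49 per arm is 0.793.

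**How often the finding occurs**

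When catheter and Exparel have the same true mean, P(non-significant) = 1 − 0.05 = 0.95. This does not depend on n, on the SD or on the control mean. Simulated trials (normal data, 49 per arm, pooled t-tests) give:

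| True means, single shot / catheter / Exparel (mg) | SDs | No difference | No difference, and neither arm significantly below single shot |
|---|---|---|---|
| 4.1 / 4.1 / 4.1 | 3 / 3 / 3 | 0.95 | 0.91 |
| 4.1 / 2.4 / 2.4 | 3 / 3 / 3 | 0.95 | 0.09 |
| 4.1 / 2.4 / 2.4 | 3 / 1.3 / 1.3 | 0.95 | 0.03 |

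The third column is the finding as the plan words it, and it is the same in every row. The fourth column shows that the information on whether the methods work lies in the comparisons with single shot. With skewed (gamma) data and equal means, the t-test gives 0.951 and the Wilcoxon test 0.949.

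**If the two methods truly differ**

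With SD 3 and 49 per arm, the chance of non-significance is 0.87, 0.72, 0.63 and 0.21 for true differences of 0.5, 0.85, 1.0 and 1.7 mg. The half-width of the 95% confidence interval is 1.985 × 3 × √(2/49) = 1.985 × 0.606 = 1.20 mg, which is 71% of the planned effect (1.20 / 1.7). A non-significant result is therefore weak evidence of similarity.

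**With a condition that both arms also be significantly below single shot**

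| Scenario | As worded | With the condition |
|---|---|---|
| All means equal, SD 3 | 0.95 | about 0.005 |
| Planned effect, SD 3 in all arms | 0.95 | 0.66 |
| Planned effect, SD 3 in single shot and 1.3 in the other two | 0.95 | 0.88 |

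At 47 per arm (53 × 0.9 = 47.7 evaluable after 10% dropout) these results move by no more than about 2.5 percentage points.

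**The case against.** The sentence is not a success rule. Success has its own sentence, which requires significantly lower opioid consumption in the catheter arm. With all arms equal, that sentence is met in about 4.5% of trials if the catheter need beat only one of the single-injection arms, and in about 0.5% if it must beat both. A reader might infer that the trial would be declared successful 95% of the time when nothing works, or 97.5% when the two statements are combined. The documents do not support this. They call the finding beneficial, not a success, and the 97.5% also needs the either-arm reading (about 95.5% otherwise). This objection stands.

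The comparisons with single shot are planned and would be reported, with Exparel versus single shot as the primary analysis. If both methods failed, the primary result would be negative. A reader might infer that such a trial would be published as positive, but nothing in the plan says so. The Publication Plan's statement that "an analysis demonstrating a statistically significant difference or no difference between any of the study arms would be useful" concerns publishability, not efficacy. This stands too. What remains is that the interpretation is not tied to those comparisons.

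The stated reason, avoiding the effort of a catheter, also holds when all arms are equal, since the catheter is then unnecessary. The gap is narrower: nothing then supports Exparel over plain single shot. The Rationale is background and not a decision rule, so the success criteria omit its expectation rather than formally contradict it.

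Finally, the 95% is simply 1 − alpha, and an equivalence margin might seem to cure the problem. How often equivalence would be concluded with all arms equal depends heavily on a margin that the plan does not give. With SD 3 and assumed margins of 1.7, 1.2, 1.0 and 0.85 mg, it is about 75%, 25%, 3.5% and below 0.1%. These figures therefore give no fixed size to the problem. The logical point survives: a margin between catheter and Exparel still does not use the control arm.

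**Conclusion.** The concern holds as a gap in a pre-stated interpretation. The finding is as likely when all three arms are equal as at the planned effect, about 95% in both cases, so on its own it says nothing about whether either method works. With all arms equal, about 91% of trials would show it with neither method significantly below single shot.

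These figures rest on three assumptions: no difference means a non-significant two-sided test; the 0.05 level applies to this comparison; and catheter and Exparel have equal true means, as the plan itself assumes. A true difference between them lowers the figure. The conclusion does not extend to a false claim of formal success or to concealment of a failed primary comparison.

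**What to change.** Add to Study success criteria:

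*Similarity of the Exparel and catheter arms will be interpreted as a benefit only if both arms also show significantly lower opioid consumption than the single shot arm in the planned comparisons. Otherwise the catheter-versus-Exparel result will be reported as an estimate with its confidence interval, and no benefit will be concluded. A non-significant difference alone will not be described as demonstrating similarity.*

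The time point and the single shot drug named in this sentence should follow the reconciled text: the Analysis Plan in section G refers to 72 hours and Ropivacaine, whereas the Primary Aim refers to 48 hours and Bupivacaine.

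The cost is a short addition to the text. No new patients, data or tests are needed, because both comparisons with single shot are already in the Statistical Analysis Plan. The downside is that when both methods work as planned, the conclusion is reached in about 66% (SD 3 in all arms) to 88% (SD 1.3 in the catheter and Exparel arms, 3 in single shot) of trials instead of 95%. When neither works, it falls from 95% to about 0.5%.
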